### 7.3.2.3 Serious

An adverse event or suspected adverse reaction is considered *serious* if, in the view of either the investigator or sponsor, it results in any of the following outcomes:

- Death
- Life-threatening adverse event
- Inpatient hospitalization or prolongation of existing hospitalization
- A persistent or significant incapacity or substantial disruption of the ability to conduct normal life function
- Important medical events that may not result in death, are life-threatening, or require hospitalization may be considered serious when, based upon appropriate medical judgment, they may jeopardize the patient or subject and may require medical or surgical intervention to prevent one of the outcomes listed in this definition. Examples of such medical events include allergic bronchospasm requiring intensive treatment in an emergency room or at home, blood dyscrasias or convulsions that do not result in inpatient hospitalization, or the development of drug dependency or drug abuse.

### 7.3.2.4 Life-threatening

An adverse event or suspected adverse reaction is considered *life-threatening* if, in the view of either the investigator or sponsor, its occurrence places the patient or subject at immediate risk of death. It does not include an adverse event or suspected adverse reaction that, had it occurred in a more severe form, might have caused death.

## 7.4 Recording of an Adverse Event

All grade 3 and above adverse events will be entered into OnCore®, whether or not the event is believed to be associated with use of the study drug. Data about these events and their severity will be recorded using the NCI CTCAE v4.0.

The Investigator will assign attribution of the possible association of the event with use of the investigational drug, and this information will be entered into OnCore® using the classification system listed below:

Relationship	Attribution	Description
Unrelated to investigational drug/intervention	Unrelated	The AE is clearly NOT related to the intervention
	Unlikely	The AE is doubtfully related to the intervention
Related to investigational drug/intervention	Possible	The AE may be related to the intervention
	Probable	The AE is likely related to the intervention
	Definite	The AE is clearly related to the intervention

Signs or symptoms reported as adverse events will be graded and recorded by the Investigator according to the CTCAE. When specific adverse events are not listed in the CTCAE they will be graded by the Investigator as *none*, *mild*, *moderate* or *severe* according to the following grades and definitions:

---

Grade 0	No AE (or within normal limits)
Grade 1	Mild; asymptomatic or mild symptoms; clinical or diagnostic observations only; intervention not indicated
Grade 2	Moderate; minimal, local, or noninvasive intervention (e.g., packing, cauter) indicated; limiting age-appropriate instrumental activities of daily living (ADL)
Grade 3:	Severe or medically significant but not immediately life-threatening; hospitalization or prolongation of hospitalization indicated; disabling; limiting self-care ADL
Grade 4:	Life-threatening consequences; urgent intervention indicated
Grade 5:	Death related to AE

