Study Drugs	
PROSTVAC (Bavarian-Nordic) is a therapeutic cancer vaccine. Two component viral vectors (PROSTVAC-V, a recombinant vaccinia vector, and PROSTVAC-F, a recombinant fowlpox vector) are used together in a prime-boost vaccination regimen. Both vectors co-express a human PSA gene and genes encoding three human immunological costimulatory molecules: B7.1, intercellular adhesion molecule-1 (ICAM-1), and leukocyte function-associated antigen-3 (LFA-3).
 
Ipilimumab (Yervoy, Bristol-Myers Squibb) is a human immunoglobulin G-1 kappa monoclonal antibody that targets cytotoxic T lymphocyte-associated antigen-4 (CTLA-4). Ipilimumab was the first in a class of therapies targeting T cell activation and regulation to be licensed in the broad category of agents known as immune checkpoint inhibitors, based on improved overall survival in patients with metastatic melanoma.

Safety Assessments	Safety will be assessed by reviewing adverse events (AEs), laboratory evaluations, and by physical examination. The NCI CTCAE v4.03 will be used. All AEs and serious AEs (SAEs), with the exception of those considered related to RP, will be recorded on case report forms (CRFs) from enrollment through 12 weeks post-surgery
Efficacy Assessments	For the primary endpoint, the change in the number of CD3+ T cell infiltration within prostate tissue between the biopsy and RP specimen will be quantified using immunohistochemistry (IHC), with a positive result if there is $\geq 2$ fold increase in the number of CD3+ T cell infiltration.  As secondary endpoints we will look at changes in T cell subsets by IHC in the tissue and circulating T cells by flow cytometry. We will assess the toxicities according to NCI CTCAE v.4.03
Unique Aspects of this Study	This is the first study to: 1) evaluate the safety of systemic PROSTVAC or ipilimumab monotherapy, or the combination of PROSTVAC and ipilimumab, in the neoadjuvant setting in prostate cancer patients; 2) evaluate their direct effect both systemically, and in the tumor microenvironment. The secondary and exploratory studies will enhance the understanding of the immune effects of these therapeutic modalities.

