### 5.3 Radical Prostatectomy

Radical Prostatectomy will be performed at least 14 days but not more than 28 days following the last scheduled subcutaneous injection of PROSTVAC-F or ipilimumab. AEs and concomitant medications will be evaluated and recorded prior to surgery. Adverse events and concomitant medications considered by the Investigator to be related to RP will be recorded in appropriate source documentation; however, such AEs and concomitant medications will not be recorded on eCRFs. Blood samples for PSA and for immune assays will be collected prior to RP.

Standard institutional practices for the care and treatment of surgical patients will be followed before, during, and after the subject's RP. Adverse events and concomitant medications considered by the Investigator to be related to RP will be recorded in appropriate source documentation but will not be recorded on a eCRF.

Patients will be informed in the written consent that radical prostatectomy may be delayed due to adverse events resulting from study treatment, at the discretion of the Investigator and performing surgeon.

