## 7.6 Adverse Events Monitoring

All adverse events, whether or not unexpected, and whether or not considered to be associated with the use of the study drug, will be entered into OnCore®, as noted above.

The Investigator will assess all adverse events and determine report ability requirements to the UCSF Data and Safety Monitoring Committee (DSMC) and UCSF's Institutional Review Board, the Committee on Human Research (CHR); and, when the study is conducted under an Investigational New Drug Application (IND), to the Food and Drug Administration (FDA) if it meets the FDA reporting criteria.

All adverse events entered into OnCore® will be reviewed by the Helen Diller Family Comprehensive Cancer Center Site Committee on a weekly basis. The Site Committee will review and discuss at each weekly meeting the selected toxicity, the toxicity grade, and the attribution of relationship of the adverse event to the administration of the study drug(s).

All grade(s) 3-5 adverse events entered into OnCore® will be reviewed on a monthly basis at the Site Committee meetings. The Site Committee will review and discuss the selected toxicity, the toxicity grade, and the attribution of relationship of the adverse event to the administration of the study drug(s).

In addition, all suspected adverse reactions considered "serious" entered into OnCore®, will be reviewed and monitored by the Data and Safety Monitoring Committee on an ongoing basis and discussed at DSMC meetings, which take place every six weeks.

For a detailed description of the Data and Safety Monitoring Plan please refer to Appendix 2.

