### 8.5.2 Secondary Analyses (or Analyses of Secondary Endpoints)

- T cell tumor infiltration (of selected T cell subsets) will be scored by IHC assessment, and scored by the number of T cells/ $\mu\text{m}^2$ . Therefore, the number of T cells will be normalized per unit area. The change in T cell infiltration following neoadjuvant therapy will be determined as described above for the primary endpoint. Similar analyses may be performed for other immune cells, such as CD4+, CD8+, CD56+, FOXP3, etc. Results will be reported as described for the primary endpoint, and T cell infiltration will be reported separately for areas of tumor interface, tumor center and benign tissue.
- Flow cytometry will be performed in both pre- and post-treatment peripheral blood mononuclear cells (PBMC) to determine the change in T cell activation (both  $\text{T}^{\text{reg}}$  and  $\text{T}^{\text{effector}}$  cells) after neoadjuvant therapy. Descriptive statistics for continuous measurements will be used to summarize the changes.
- Treatment-related toxicities will be assessed according to NCI CTCAE v4.03, for all patients who receive at least a single dose of investigational therapy. The distribution for the

maximum observed grade for each adverse event will be tabulated and reported with 95% confidence interval.

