## 9.6 Case Report Forms (CRFs)

The Principal Investigator and/or his/her designee, will prepare and maintain adequate and accurate participant case histories with observations and data pertinent to the study. Study specific electronic Case Report Forms (eCRFs) will document safety and treatment outcomes for safety monitoring and data analysis. All study data will be entered into OnCore® via standardized eCRFs in accordance with the CTMS study calendar, using single data entry with a secure access account. The Clinical Research Coordinator (CRC) will complete the eCRFs as soon as possible upon completion of the study visit; the Investigator will review and approve the completed eCRFs.

The information collected on eCRFs shall be identical to that appearing in original source documents. Source documents will be found in the patient's medical records maintained by UCSF personnel. All source documentation should be kept in separate research folders for each patient.

In accordance with federal regulations, the Investigator is responsible for the accuracy and authenticity of all clinical and laboratory data entered onto eCRFs. The PI will approve all completed eCRFs to attest that the information contained on the eCRFs is true and accurate.

All source documentation and CTMS data will be available for review/monitoring by the UCSF DSMC and regulatory agencies.

The Principal Investigator will be responsible for ensuring the accurate capture of study data. At study completion, when the eCRFs have been declared to be complete and accurate, the database will be locked. Any changes to the data entered into the eCRFs after that time can only be made by joint written agreement among the Study Chair, the Trial Statistician, and the Protocol Project Manager.

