#### 3. Review and Oversight Requirements

##### 3.1 Adverse Event Monitoring

All Grade 3-5 Adverse Events (AEs), whether or not considered to be expected or unexpected and whether or not considered to be associated with the use of the study drug, will be entered into OnCore®, UCSF's Clinical Trial Management System.

Adverse Events are graded according to the Common Terminology Criteria for Adverse Events (CTCAE) (version 4.03) as developed and revised by the Common Therapy Evaluation Program (CTEP) of the National Cancer Institute. Adverse events are further given an assignment of attribution or relationship to treatment or medical procedure. Attribution categories are:

- **Definite** – The adverse event is clearly related to the investigational agent(s) or medical procedure.
- **Probable** – The adverse event is likely related to the investigational agent(s) or medical procedure.
- **Possible** – The adverse event may be related to the investigational agent(s) or medical procedure.

- **Unlikely** – The adverse event is doubtfully related to the investigational agent(s) or medical procedure.
- **Unrelated** – the adverse event is clearly not related to the investigational agent(s) or medical procedure.

All Grade 3-5 adverse events entered into OnCore® will be reviewed on a monthly basis at the Site Committee meetings. The Site Committee will review and discuss the selected toxicity, the toxicity grade, and the attribution of relationship of the adverse event to the administration of the study drug(s).

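### Adverse-event capture rules conflict for one database: grade 3 and above or all grades, and events attributed to prostatectomy kept in or left out

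*Combined protocol and SAP*

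**What the plan says.** Four places set out which adverse events (AEs) are recorded.

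- Section 7.4: "All grade 3 and above adverse events will be entered into OnCore", whatever the relation to study drug.
- Appendix 2, 3.1: "All Grade 3-5 Adverse Events (AEs), whether or not considered to be expected or unexpected", again into OnCore.
- Section 7.6: "All adverse events, whether or not unexpected, and whether or not considered to be associated with the use of the study drug, will be entered"; the destination is again OnCore. It refers back to what was said above, but what stands above is the grade 3 rule of 7.4.
- Abstract, Safety Assessments: "All AEs and serious AEs (SAEs), with the exception of those considered related to RP, will be recorded on case report forms (CRFs", from enrollment to 12 weeks after surgery.

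Section 5.3 adds that, for events the investigator considers related to RP, "such AEs and concomitant medications will not be recorded on eCRFs"; they stay in source documents. Appendix 2, 3.2 puts every serious AE into OnCore and states no exception for RP.

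Section 9.6 ties these together: "All study data will be entered into OnCore" through standardized eCRFs. The Abstract's CRF and the OnCore of 7.4 and 7.6 are therefore the same data set.

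On the analysis side, 2.4.2 lists treatment-related toxicity by CTCAE with no grade limit. Section 8.5.2 says that the distribution of the "maximum observed grade for each adverse event will be tabulated" with a 95% confidence interval, and 8.7 tabulates every toxicity observed, by arm and in aggregate.

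**The concern.** Safety in the neoadjuvant setting is a secondary objective, and the Abstract presents the trial as the first to study it for these agents. The planned tables need all grades. Staff who take 7.4 or Appendix 2 as the operating instruction would supply grades 3 to 5 only, and the maximum-grade distribution would then be truncated.

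Grade 2 events also matter in the conduct of the trial. Under 5.2.1, some of them lead to a skipped ipilimumab dose, so the event that explains a missed dose could be absent from the AE data.

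The RP exception raises a different problem. The trial is open-label, and whether a peri-operative event reaches the eCRF depends on the investigator's view of its cause. If study drug made a surgical complication worse and it was labelled surgical, it could be missing from the by-arm tables. It could also be missing from the later criterion in 5.1.1, which counts grade 3 or higher events as a percentage of patients without repeating the restriction to treatment-associated events. No surgical-safety endpoint is listed that would pick it up.

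**Working it through.** The plan gives no figure on this point to reproduce. The check is a reconciliation of the text, followed by an illustration of size.

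**Rules side by side**

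| Place | Grades | Attribution | Destination |
|---|---|---|---|
| 7.4 | 3 and above | any | OnCore |
| Appendix 2, 3.1 | 3 to 5 | any | OnCore |
| 7.6 | no limit | any | OnCore |
| Abstract | no limit, AEs and serious AEs | RP-related excluded | CRF |
| 5.3 | no limit | RP-related excluded | source documents only |
| Appendix 2, 3.2 | all serious AEs | no RP exception | OnCore |

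**Three test cases**

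1. A non-serious grade 2 event before surgery. Sections 7.6 and the Abstract require it; 7.4 and Appendix 2, 3.1 do not call for it.
2. A grade 3 event after surgery that the investigator attributes to RP. Sections 7.4, 7.6 and Appendix 2, 3.1 require it; 5.3 and the Abstract exclude it.
3. A serious event attributed to RP. Appendix 2, 3.2 requires it; the Abstract excludes it.

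The first case decides whether 8.5.2 and 8.7 can be complete. The second and third decide whether peri-operative events appear by arm.

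**Size of the loss if the grade 3 rule is followed**

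The share of affected patients with no immune-related AE (irAE) on file is 1 − (rate of grade 3–4) / (rate of any grade). The rates are background figures in 1.3.2, 1.3.3 and 1.3.4, used here as assumptions.

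- Melanoma phase III trial, 3 mg/kg (1.3.2): about 60% any grade; grade 3–4 is 12.2% + 2.3% = 14.5%. 1 − 14.5/60 = 76%. With 14 patients per arm, 0.60 × 14 = 8.4 patients would be expected to have an irAE and 0.145 × 14 = 2.0 would be on file.
- The same trial with the rounded 10–15% for grade 3–4: 1 − 15/60 = 75% to 1 − 10/60 = 83%.
- Dose-ranging data at 3 mg/kg: with 56% any grade and 7% grade 3–4 (1.3.2), 1 − 7/56 = 87.5%. With 46/71 = 65% any grade (1.3.4), 1 − 7/65 = 89%.
- Prior phase I trial of PROSTVAC plus ipilimumab, 30 patients (1.3.3): 21 had a grade 2 or higher irAE and 8 had grade 3 or 4. 21 − 8 = 13 patients (13/21 = 62%) would have no irAE on file. The reported injection-site reactions were grade 1 in 3 patients and grade 2 in 26; all 3 + 26 = 29 would be missed.

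Under the all-grades rule of 7.6 none of this is lost, apart from events removed by the RP exception.

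**The case against.** The strongest reply is that 7.4 sets a minimum. It does not say that only grade 3 and above are entered, and it goes on to define grades 1 and 2 for events the investigator records. Section 7.6 separates a weekly review of all AEs from a monthly review of grades 3 to 5, which presupposes lower grades in the database. Section 5.6.5 requires suspected irAEs on a form with no grade limit, and 7.7 transfers all non-serious AEs to the companies. Standardized eCRFs (9.6) limit how far sites can diverge. This stands to the extent that a complete table is achievable. It does not remove the conflict, because two places name a threshold and two do not.

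On surgery, the listed endpoint is treatment-related toxicity, so leaving out purely surgical events fits its wording. Post-operative AE evaluation is scheduled, and RP-attributed events remain in source documents. That also stands. What remains is that attribution is judged open-label and the texts disagree.

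A reader might infer more than the documents support:

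- That the maximum-grade table cannot be produced. It can be under 7.6 or, apart from RP-attributed events, under the Abstract; under 7.4 it would be truncated.
- That surgical harm is left out altogether. Sections 7.4, 7.6 and Appendix 2 would admit severe or serious surgical events.
- That the grade cut-off undermines the arm-discontinuation rule. That rule counts grade 3 or higher events, which 7.4, 7.6 and Appendix 2 all capture; only the RP exception could affect it, and the criterion for the first six patients is limited to treatment-associated events.
- That the arms cannot be compared. Randomization is in blocks, no testing of AEs is planned (8.7), and a difference in site practice does not by itself follow arm.

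**Conclusion.** The point holds as an internal inconsistency that should be fixed. The capture rules differ by grade and by RP attribution for one database, and they determine what the secondary safety analysis contains. The primary CD3+ endpoint is not affected, and the safety analysis is descriptive.

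The size depends on which rule is followed. If 7.4 and Appendix 2, 3.1 are followed, grades 1 and 2 are lost; on the background rates, 75% to 89% of patients with an irAE would have none on file, with 76% from the phase III figures. These figures are illustrative. They come from metastatic melanoma, and section 1.3.4 itself warns that earlier AE data may not apply with two doses. The combination-trial counts come from metastatic castration-resistant disease, with several ipilimumab doses and added GM-CSF. The size of the RP-related gap cannot be estimated from the documents; they establish only that a peri-operative event worsened by study drug may be missing.

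**What to change.** Amend 7.4 and Appendix 2 (3.1) so that AEs of all grades are entered in OnCore, in line with 7.6 and the Abstract. Start at enrollment, as in the Abstract, and state one end date: the Abstract stops at 12 weeks after surgery, while 6.1.7 still evaluates AEs at 6 and 12 months.

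Reconcile 5.3 and the Abstract with 7.4 and Appendix 2 so that grade 3 or higher and serious peri-operative events go on the eCRF whatever the attribution. Record attribution to study drug and attribution to RP as separate items, and add a by-arm table of these events to 8.7.

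The cost is a short amendment and modest extra data entry for 42 patients. RP-related events are already in source documents, so no new assessments are needed.

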## 7.5 Follow-up of Adverse Events

All adverse events will be followed with appropriate medical management until resolved. Patients removed from study for unacceptable adverse events will be followed until resolution or stabilization of the adverse event. For selected adverse events for which administration of the investigational drug was stopped, a re-challenge of the subject with the investigational drug may be conducted if considered both safe and ethical by the Investigator.

## 7.6 Adverse Events Monitoring

All adverse events, whether or not unexpected, and whether or not considered to be associated with the use of the study drug, will be entered into OnCore®, as noted above.

The Investigator will assess all adverse events and determine report ability requirements to the UCSF Data and Safety Monitoring Committee (DSMC) and UCSF's Institutional Review Board, the Committee on Human Research (CHR); and, when the study is conducted under an Investigational New Drug Application (IND), to the Food and Drug Administration (FDA) if it meets the FDA reporting criteria.

All adverse events entered into OnCore® will be reviewed by the Helen Diller Family Comprehensive Cancer Center Site Committee on a weekly basis. The Site Committee will review and discuss at each weekly meeting the selected toxicity, the toxicity grade, and the attribution of relationship of the adverse event to the administration of the study drug(s).

All grade(s) 3-5 adverse events entered into OnCore® will be reviewed on a monthly basis at the Site Committee meetings. The Site Committee will review and discuss the selected toxicity, the toxicity grade, and the attribution of relationship of the adverse event to the administration of the study drug(s).

In addition, all suspected adverse reactions considered "serious" entered into OnCore®, will be reviewed and monitored by the Data and Safety Monitoring Committee on an ongoing basis and discussed at DSMC meetings, which take place every six weeks.

For a detailed description of the Data and Safety Monitoring Plan please refer to Appendix 2.

## 7.7 Expedited Reporting

### Reporting to the Data and Safety Monitoring Committee

If a death occurs during the treatment phase of the study or within 30 days after the last administration of the study drug(s) and it is determined to be related either to the study drug(s) or to a study procedure, the Investigator or his/her designee must notify the DSMC Chair (or qualified alternate) within 1 business day of knowledge of the event. The contact may be by phone or e-mail.

